11.1.4 Response Criteria

11.1.4.1 Evaluation of Target Lesions

Complete Response (CR): Disappearance of all target lesions. Any pathological lymph nodes (whether target or non-target) must have reduction in short axis to <10 mm.

Partial Response (PR): At least a 30% decrease in the sum of the diameters of target lesions, taking as reference the baseline sum diameters.

Progressive Disease (PD): At least a 20% increase in the sum of the diameters of target lesions, taking as reference the smallest sum on study (this includes the baseline sum if that is the smallest on study). In addition to the relative increase of 20%, the sum must also demonstrate an absolute increase of at least 5 mm. (Note: the appearance of one or more new lesions is also considered progression, even if the sum of the diameters of the other target lesions has not increased by 20%).

Stable Disease (SD): Neither sufficient shrinkage to qualify for PR nor sufficient increase to qualify for PD, taking as reference the smallest sum of the diameters while on study.

11.1.4.2 Evaluation of Non-Target Lesions

Complete Response (CR): Disappearance of all non-target lesions and normalization of tumor marker level. All lymph nodes must be non-pathological in size (<10 mm short axis).

Note: If tumor markers are initially above the upper normal limit, they must normalize for a patient to be considered in complete clinical response.

Non-CR/Non-PD: Persistence of one or more non-target lesion(s) and/or maintenance of tumor marker level above the normal limits.

Progressive Disease (PD): Appearance of one or more new lesions and/or *unequivocal progression* of existing non-target lesions. Unequivocal progression should not normally trump target lesion status. It must be representative of overall disease status change, not a single lesion increase.

Although a clear progression of “non-target” lesions only is exceptional, the opinion of the treating physician should prevail in such circumstances, and the progression status should be confirmed at a later time by the Principal Investigator and/or review panel.

11.1.4.3 Evaluation of Best Overall Response

The best overall response is the best response recorded from the start of the treatment until disease progression/recurrence (taking as reference for progressive disease the smallest measurements recorded since the treatment started). The patient's best response assignment will depend on the achievement of both measurement and confirmation criteria.

For Patients with Measurable Disease (*i.e.*, Target Disease) +/- Non-Target Disease

Target Lesions	Non-Target Lesions	New Lesions*	Overall Response	Best Overall Response when Confirmation is Required*
CR	CR	No	CR	≥4 wks. Confirmation**
CR	Non-CR/Non-PD	No	PR	≥4 wks. Confirmation**
CR	Not evaluated	No	PR	
PR	Non-CR/Non-PD/not evaluated	No	PR	
SD	Non-CR/Non-PD/not evaluated	No	SD	Documented at least once ≥4 wks. from baseline**
PD	Any	Yes or No	PD	no prior SD, PR or CR
Any	PD***	Yes or No	PD	
Any	Any	Yes	PD	

* See RECIST 1.1 manuscript for further details on what is evidence of a new lesion. ** Only for non-randomized trials with response as primary endpoint. (Not applicable in this trial). *** In exceptional circumstances, unequivocal progression in non-target lesions may be accepted as disease progression.
 
Note: Patients with a global deterioration of health status requiring discontinuation of treatment without objective evidence of disease progression at that time should be reported as “symptomatic deterioration.” Every effort should be made to document the objective progression even after discontinuation of treatment, based on intention to treat analysis.
				

For Patients with Non-Measurable Disease Only (*i.e.*, Non-Target Disease)

Non-Target Lesions	New Lesions	Overall Response
CR	No	CR
Non-CR/non-PD	No	Non-CR/non-PD*
Not all evaluated	No	not evaluated
Unequivocal PD	Yes or No	PD
Any	Yes	PD

* ‘Non-CR/non-PD’ is preferred over ‘stable disease’ for non-target disease. As SD is increasingly used as an endpoint for assessment of efficacy in some trials, to assign this category when no lesions can be measured is not advised.
		

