1.2 OBJECTIVES

1.2.1 Primary Objectives:

1. To evaluate the progression-free survival (PFS) of fulvestrant or exemestane with or without ribociclib after progression on anti-estrogen therapy plus cyclin-dependent kinase 4/6 inhibitor in patients with hormone receptor positive (HR+), HER2- breast cancer.

- **Endpoint: PFS.** Defined as the interval from time of randomization until objective disease progression (local assessment) or death from any cause. Kaplan-Meier estimates will be used to calculate medians and 95% confidence intervals for PFS. A one-sided log-rank test will be used to test for a difference in PFS between the two arms.

1.2.2 Secondary/Exploratory Objectives:

1. To assess the Overall Response Rate (ORR = complete + partial response rate) and Clinical Benefit Rate (CBR= ORR + stable disease rate at ≥ 24 weeks of follow up) in the study population in both arms of the trial, post-randomization.

- **Endpoints: ORR, CBR.** Evaluation of disease will be made according to RECIST criteria (version 1.1) in patients with measurable disease. As this study will enroll patients with measurable and un-measurable disease as defined by RECIST v1.1, ORR will only be assessed in evaluable patients. CBR will also be determined. Patients with non-measurable disease only can be categorized as ‘complete response’, ‘non-complete response’, ‘non-progressive disease’, or ‘progressive disease’, but are sometimes not evaluable. (Section 11.1.4.2: Evaluation of Non-Target Lesions).
 - **Duration of overall response:** The duration of overall response is measured as the time interval from when measurement criteria are met for complete or partial response (whichever is first recorded) until the first date that recurrent or progressive disease is objectively documented
2. For patients in registration scenario #1, to assess the PFS, ORR, CBR, and safety of ribociclib with an aromatase inhibitor in patients with metastatic or unresectable HR+ HER2- breast cancer. This analysis will be based on data collected in the pre-randomization component of the trial for patients registered under scenario #1. There is no comparator arm for this component of the trial, but it will add to the available clinical safety and efficacy data with ribociclib + AI in this population.

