3. PATIENT SELECTION

3.1 Inclusion Criteria:

A subject **must meet all of the following criteria** to be eligible for the study:

- Men or women at least 18 years of age with histologically or cytologically confirmed adenocarcinoma of the breast with unresectable or metastatic disease.
- Most recent tumor biopsy or surgical resection specimen must be either ER positive, PgR positive, or both, as defined by immunohistochemistry (IHC) $\geq 1\%$ (as per the ASCO-CAP guidelines).⁸⁵
- HER2-negative breast cancer defined as a negative in situ hybridization test or an IHC status of 0 or 1+. If IHC is 2+ (i.e. indeterminate), a negative in situ hybridization (FISH, CISH, or SISH) test is required by local laboratory testing. (as per the ASCO-CAP guidelines).⁸⁶
- Postmenopausal status **or** receiving ovarian ablation with a GnRH agonist such as goserelin. Postmenopausal status is defined by any one of the following criteria:
 - Prior bilateral oophorectomy.
 - Age ≥ 60 years.
 - Age < 60 and amenorrhea for 12 or more months (in the absence of chemotherapy, tamoxifen, toremifen, or ovarian suppression) and FSH, LH, and estradiol in the postmenopausal range per local normal.

If the patient does not meet criteria for postmenopausal status but is receiving ovarian ablation therapy with a gonadotropin-releasing hormone (GnRH) agonist such as goserelin, the patient is eligible for this study, provided that the GnRH agonist is started at least 2 weeks prior to C1D1 of anti-estrogen therapy.

- Have evidence of measurable or unmeasurable disease.
- Eastern Cooperative Group (ECOG) performance status of 0 **or** 1. (Appendix A)
- Scenario 1: No prior cdk 4/6 inhibitor (Closed to Accrual). If patient has not previously received letrozole, letrozole will be supplied by Novartis. If previously progressed on letrozole, another aromatase inhibitor that the patient has not previously received is allowed, per standard of care (anastrozole or exemestane, not supplied by study). Ribociclib will be supplied by Novartis. If patient has previously received letrozole, anastrozole, and exemestane, (s)he is not eligible. For scenario 1, patients are allowed to have started the aromatase inhibitor within 4 consecutive weeks prior to protocol registration. For instance, it is acceptable for patient who will be treated with letrozole in scenario #1, to have started letrozole within 4 consecutive weeks prior to protocol registration. No prior fulvestrant allowed.

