11.1.2 Disease Parameters

Measurable disease: Measurable lesions are defined as those that can be accurately measured in at least one dimension (longest diameter to be recorded) as ≥ 20 mm by chest x-ray or as ≥ 10 mm with CT scan, MRI, or calipers by clinical exam. All tumor measurements must be recorded in millimeters (or decimal fractions of centimeters).

Note: Tumor lesions that are situated in a previously irradiated area may be considered measurable, as long as they meet the criteria above.

Malignant lymph nodes: To be considered pathologically enlarged and measurable, a lymph node must be ≥ 15 mm in short axis when assessed by CT scan (CT scan slice thickness recommended to be no greater than 5 mm). At baseline and in follow-up, only the short axis will be measured and followed.

Non-measurable disease: All other lesions (or sites of disease), including small lesions (longest diameter < 10 mm or pathological lymph nodes with ≥ 10 to < 15 mm short axis), are considered non-measurable disease. Bone lesions, leptomeningeal disease, ascites, pleural/pericardial effusions, lymphangitis cutis/pulmonitis, inflammatory breast disease, and abdominal masses (not followed by CT or MRI), are considered as non-measurable.

Note: Cystic lesions that meet the criteria for radiographically defined simple cysts should not be considered as malignant lesions (neither measurable nor non-measurable) since they are, by definition, simple cysts.

‘Cystic lesions’ thought to represent cystic metastases can be considered as measurable lesions, if they meet the definition of measurability described above. However, if non-cystic lesions are present in the same patient, these are preferred for selection as target lesions.

Target lesions: All measurable lesions up to a maximum of 2 lesions per organ and 5 lesions in total, representative of all involved organs, should be identified as **target lesions** and recorded and measured at baseline. Target lesions should be selected on the basis of their size (lesions with the longest diameter), be

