***** Please see Appendix F for Guidelines for Affiliate Institutions for Registration and Data Reporting Requirements.**

13. STATISTICAL CONSIDERATIONS

13.1 Study Design/Primary Endpoint (Sample Size: N=120 randomized evaluable patients)

This is a multi-center phase II, randomized, double-blinded, placebo-controlled trial to evaluate the efficacy of fulvestrant (or exemestane) with or without ribociclib in patients who have previously progressed on an aromatase inhibitor (preferably letrozole) plus CDK4/6 inhibitor (ribociclib or palbociclib or abemaciclib).

Primary Endpoint

The primary endpoint is progression free survival, defined as the time from randomization to the development of progressive disease or death.

Disease status will be assessed with comprehensive radiographic studies every three treatment cycles (approximately every 12 weeks (+/- 1 week), but the development of new signs or symptoms of disease in between scheduled evaluations may prompt off-schedule radiographic or non-radiographic evaluations. Disease status will be assessed based on RECIST 1.1 criteria for measurable (target) and non-measurable (non-target) disease, as outlined in detail in Section 11.

Secondary Endpoints:

All secondary endpoints, including overall response rate (complete response + partial response rates), clinical benefit rate (overall response rate + stable disease rate), overall survival, duration of response, adverse event rate, and biomarker assessment are exploratory in nature. In addition, patients registered under scenario #1 will be assessed for progression free survival, overall response rate, clinical benefit rate, and safety while receiving ribociclib with an aromatase inhibitor (pre-randomization). As there is no comparator arm for this pre-randomization part of the study, further statistical analyses on these will not be possible.

Response rates will be estimated as the proportion of enrolled patients who achieve response, as defined in Section 11. Patients who are lost to follow-up without a valid response assessment will be classified as non-responders.

Statistical analysis:

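### The plan does not say how lasting non-CR/non-PD counts in the clinical benefit rate, and its sections disagree on whether patients with non-measurable disease only belong in the denominator

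*Combined protocol and SAP*

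**What the plan says.** **Eligibility.** Section 3.1 does not require measurable disease: "Have evidence of measurable or unmeasurable disease". Section 11.1.2 lists bone lesions, effusions and several other sites that "are considered as non-measurable".

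**CBR definition.** Section 1.2.2 gives "CBR= ORR + stable disease rate at ≥ 24 weeks of follow up". Section 13.1 gives "clinical benefit rate (overall response rate + stable disease rate", with no time limit. Neither names non-CR/non-PD.

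**Stable disease.** Section 11.1.4.1 defines it as "Neither sufficient shrinkage to qualify for PR nor sufficient increase to qualify for PD, taking as reference the smallest sum of the diameters". For patients with no measurable lesion, the second table in Section 11.1.4.3 offers only CR, non-CR/non-PD, not evaluated, or PD. Its footnote prefers non-CR/non-PD to stable disease and adds that "to assign this category when no lesions can be measured is not advised".

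**Denominator.** Section 13.1 states: "Response rates will be estimated as the proportion of enrolled patients who achieve response, as defined in Section 11". It also applies the intention-to-treat principle to primary and secondary outcomes other than safety. In Section 1.2.3, the row for comparing ORR and CBR describes the endpoint as response and stable disease rates in patients with measurable disease. Section 1.2.2 sets the objective for the study population in both arms, ties RECIST evaluation to measurable disease, limits ORR to evaluable patients, and says that CBR will be determined as well, without naming its denominator.

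**Status.** Section 13.1 calls all secondary endpoints exploratory.

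**The concern.** Take a patient with bone-only disease who is scanned on schedule and stays non-CR/non-PD for a year. Clinically this is lasting disease control, which CBR is meant to capture. Under the written rules the patient cannot be PR or SD, since both need target lesions, and so cannot enter the CBR numerator short of a complete response.

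What happens next depends on which section the analyst follows: the patient is counted as no benefit, or is left out although randomized. The first choice lowers CBR in both arms and makes it depend on the mix of disease types. The second gives up part of the randomized comparison.

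This is separate from the missing 24-week limit in Section 13.1 and from the rule for patients without a valid assessment. It concerns patients who are fully assessed and pass 24 weeks.

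**Working it through.** The documents give no CBR rate, target or power, so there is no CBR figure to reproduce. The check has two parts.

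**1. The same patient under each section**

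The patient has non-measurable disease only and is non-CR/non-PD for at least 24 weeks.

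| Source | In denominator? | In numerator? |
|---|---|---|
| 13.1 (enrolled patients, intention to treat) | Yes | No |
| 1.2.3 (measurable disease) | No | No |
| 1.2.2 (study population; no denominator named for CBR) | Not stated | Not stated |

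Section 11.1.1 does define a set evaluable for non-target disease, but nothing links that set to CBR.

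**2. Illustration of size**

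Inputs from the sample size justification in Section 13.1: median PFS 3.8 months (control) and 6.5 months (ribociclib), and 120 randomized patients at 1:1, so 60 per arm.

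Assumptions, none of them given in the documents for this purpose:
- exponential PFS;
- the same PFS in measurable and non-measurable disease;
- no complete response in patients with non-measurable disease only;
- a share p of such patients of 20% to 40%, equal in both arms.

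Time point: 24 × 7 / 30.4375 = 5.52 months.

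Progression-free proportion at 24 weeks, S = exp(−ln 2 × 5.52 / median):
- Control: exp(−0.6931 × 5.52 / 3.8) = 0.365
- Ribociclib: exp(−0.6931 × 5.52 / 6.5) = 0.555
- Difference: 19.0 points

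This is what CBR would show if lasting non-CR/non-PD counted as benefit in all randomized patients.

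*Section 13.1 reading.* CBR = (1 − p) × S, with 60 per arm in the denominator. The number scored as no benefit although progression-free at 24 weeks is 60 × p × S.

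| p | Control | Ribociclib | Difference (points) | Progression-free but scored as no benefit, control / ribociclib |
|---|---|---|---|---|
| 20% | 29.2% | 44.4% | 15.2 | 4.4 / 6.7 |
| 30% | 25.6% | 38.9% | 13.3 | 6.6 / 10.0 |
| 40% | 21.9% | 33.3% | 11.4 | 8.8 / 13.3 |

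Both arms are multiplied by the same (1 − p), so the ratio between arms stays at 0.555 / 0.365 = 1.52.

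*Section 1.2.3 reading.* The rates stay at 36.5% and 55.5%, but 60 × p patients per arm leave the analysis: 12 at p = 20% and 24 at p = 40%, leaving 48 down to 36 per arm.

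*Imbalance with no treatment effect (Section 13.1 reading).* With the control rate in both arms and p of 30% in one and 20% in the other, CBR reads 0.70 × 0.365 = 25.6% and 0.80 × 0.365 = 29.2%, a shift of just under 4 points.

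**The case against.** A reader might infer that the plan scores every patient with lasting non-CR/non-PD as a failure, and hence that CBR is biased downwards as written. The documents do not support so flat a statement.

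- The table in Section 1.2.3 restricts the endpoint to measurable disease, and Section 1.2.2 ties RECIST evaluation to the same patients. On that text these patients are outside the analysis and nobody is mis-scored.
- The enrolled-patients sentence in Section 13.1 is about response as defined in Section 11, and Section 11 does not define CBR. Carrying it over to CBR is an inference. The general intention-to-treat statement supports that inference but conflicts with Section 1.2.3.
- The footnote in Section 11.1.4.3 advises against SD and does not prohibit it. Section 1.2.2 also lists the categories for non-measurable disease directly after saying that CBR will be determined, so these patients were in view.
- Section 11.1.6 defines the percentage progression-free at 24 weeks, which would count these patients properly.

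The first two points stand, and they limit the finding to an undefined rule and a conflicting denominator. The others help less. SD as defined still needs a sum of target-lesion diameters, so a site that assigns it without target lesions departs from the plan's own definition, and sites may differ. Listing the categories does not say which of them count as benefit. The 24-week progression-free percentage is not among the listed objectives. Neither reading credits the patient with benefit.

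**Conclusion.** The handling of lasting non-CR/non-PD in CBR is undefined, and Sections 1.2.2, 1.2.3 and 13.1 do not agree on who is in the denominator. Following the stated categories, a fully assessed patient with non-measurable disease only cannot enter the numerator short of CR.

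On the intention-to-treat reading the illustrative absolute difference falls from 19.0 points to between 15.2 and 11.4, with the ratio between arms unchanged. On the measurable-disease reading there is no such understatement, but one fifth to two fifths of each arm is lost. These sizes depend on the assumed share, on equal PFS in both disease types and on no CR in non-measurable disease; they illustrate the issue and do not predict the trial's result.

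The impact is limited. CBR is exploratory, with no power or target rate attached. Primary PFS is unaffected, because progression is defined for non-target disease in Sections 11.1.4.2 and 11.1.4.3. The rule should still be settled before analysis. Section 13.6 records that Scenario 2 patients on treatment were unblinded in August 2023, so a rule left open could be chosen with their allocation known.

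**What to change.** In Sections 1.2.2, 1.2.3 and 13.1, use one definition: CBR is the proportion of all randomized patients with CR, PR, or SD (or, in patients with non-measurable disease only, non-CR/non-PD) lasting at least 24 weeks from randomization. The table in Section 1.2.3 must be changed too; otherwise its restriction to measurable disease would contradict the new definition.

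Align the response-rate sentence in Section 13.1 with Sections 1.2.2 and 11.1.1, so that ORR is reported in patients with measurable disease at baseline.

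The cost is a sentence in each of three places. The footnotes to the study calendar in Section 10 already require overall disease status per RECIST to be documented at each restaging, so no new data collection is needed.

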11.1.5 Duration of Response

Duration of overall response: The duration of overall response is measured from the time measurement criteria are met for CR or PR (whichever is first recorded) until the first date that recurrent or progressive disease is objectively documented (taking as reference for progressive disease the smallest measurements recorded since the treatment started).

The duration of overall CR is measured from the time measurement criteria are first met for CR until the first date that progressive disease is objectively documented.

Duration of stable disease: Stable disease is measured from the start of the treatment until the criteria for progression are met, taking as reference the smallest measurements recorded since the treatment started, including the baseline measurements.

11.1.6 Progression-Free Survival

PFS is defined as the duration of time from start of treatment to time of progression or death, whichever occurs first.

Percent progression-free at 24 weeks is defined as the proportion of patients who remain progression-free at 24 weeks from study entry day #1 (binary proportion). For the primary outcome measure in this study, because patients will be registered under two different scenarios, PFS will be measured using the date of randomization as day #1.

11.1.7 Response Review

All responses are reviewed by an expert(s) independent of the study at the study's completion. Simultaneous review of the patients' files and radiological images is the best approach.

11.2 Safety Assessment

11.2.1 Safety

While on study patients will undergo a) standard of care history and physical exam and b) standard of care blood work including complete blood count with differential, liver function tests, and serum chemistry -- at baseline, at the beginning of each treatment cycle, at time of disease progression in patients registered under scenario#1, and at a final visit when patient is off-study. (4 weeks after final treatment). A standard comprehensive adverse event assessment will be performed at the beginning of each treatment cycle. In addition, radiological studies performed for response assessment will occasionally detect asymptomatic adverse events or provide adjunct information in the case of symptomatic adverse events.

Adverse events will be graded based on the Common Terminology Criteria for Adverse Events (CTCAE) version 4.0.

